Preliminary evidence of efficacy: Although severe acute post-operative pain is not the only risk factor for chronic post-surgical pain (CPSP), an intervention that does not decrease postoperative pain is unlikely to have a significant impact on CPSP. If the 80%

confidence interval for the between-group difference in average pain score in the 24-hour postoperative period favours LA block, we will consider that preliminary evidence of efficacy.^{65,66}

Secondary outcomes of the pilot trial include adverse events related to study interventions. We will also collect the outcomes for the definitive trial to test and refine data collection processes.

The primary outcome in the definitive trial is chronic pain, defined by the Pain Burden Index, measured at 3 and 6 months following surgery. The Pain burden Index examines postsurgical pain in four postoperative body areas. The Index is calculated as a sum of the four locations (breast, chest, axilla, arm) multiplied by the frequency of pain¹² (see Form 8: Pain Burden Index).

Secondary outcomes of the definitive trial include:

- Opioid analgesia requirements during surgery and in the first 24 hours after surgery, defined as morphine milligram equivalents (MME). The total MME will include intraoperative opioids administered in the OR and postoperative opioids administered/ingested in the Postanesthetic Care Unit (PACU), Surgical Day Care Unit (SDC), Inpatient Unit, and home in the 24-hour period after completion of surgery. Opioids consumed will be converted to MME (see Appendix 3: Calculation of Morphine Milligram Equivalents (MME)).
- Acute patient-reported pain scores:
 - Numerical Rating Scale (NRS; 11-point scale) measured at the standard time points of nursing care assessments: preoperatively (baseline); four times per hour in PACU until discharge; if admitted, hourly for 2 hours, and then every 6 hours in the Inpatient Unit; and at discharge from hospital; 24 hours after surgery is complete.
- Opioid-induced side effects:
 - Postoperative nausea and vomiting
 - Nausea severity (by Verbal Rating Scale) in PACU
 - Vomiting episodes (0-48 hours after surgery) in PACU & home
- Quality of recovery (Form 7: Quality of Recovery-15 Questionnaire)

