 - Measured with the Quality of Recovery-15 (QoR-15) scores at baseline prior to surgery and 24 hours after surgery⁶⁷⁻⁶⁹. This 15-item questionnaire assesses patient-reported pain, physical comfort, physical independence, psychological support, and emotional state.⁶⁹ It takes an average of 2.5 minutes to complete. The QoR-15 has been statistically validated and is designed for both ambulatory and inpatient surgery populations.^{68,70}
- Length of stay (LOS) in hours in hospital

- Measured from the time admitted to PACU to the time discharged from hospital. LOS includes time in the PACU, Surgical Day Care (SDC) and, if required, Inpatient Unit. Patients are transferred between units and discharged from hospital according to standardized institutional criteria (see Appendix 4: PACU and SDC Discharge criteria).
- Time-based outcome measures:
 - time to perform ultrasound-guided TPVB+
 - time under general anesthesia
 - time in PACU
 - failure of discharge from PACU and requiring admission
- Rescue medications:
 - Need for rescue opioid analgesics and anti-emetics
 - Rescue medications are defined as those required “as needed” (ie, beyond scheduled) in the PACU, ward, and after discharge
 - Time to rescue opioid analgesics and anti-emetics
- Failure of early discharge:
 - Emergency room visits within 48 hours of discharge
- Complications and adverse events
 - Related to the ultrasound-guided regional block: vascular or nerve injury, Horner’s syndrome, bleeding/hematoma, local anesthetic systemic toxicity, pneumothorax, distortion tissue planes during axillary dissection, and other.
 - Related to the surgery: hematoma, tissue necrosis, urgent unplanned return to the operative theater within 24 hours of surgery.

These measures are listed in Form 6: Clinical Form and Form 11: Data Collection Form.

Sample Size

240 IBR procedures are performed annually at MSJH, 50% participation yields ~ 30 patients in 3 months. Assuming a difference of 1 and standard deviation of 1.2, this sample size yields > 80% probability that the lower bound will exclude 0.⁴⁵

Additional Details of Study Design

Participants will also be given at the time of consent a post operative package. This will contain the Quality of Recovery-15 Questionnaire (Form 7), Recovery Booklet (Form 5) and Pain Burden Index (Form 8).

The Quality of Recovery-15 Questionnaire (see Form 7) is to be completed at 24 hours after surgery in paper format or electronic format (based on their preference). This

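### For patients discharged the same day, the visible NRS schedule leaves pain between discharge and 24 h unobserved, and the source of the 24 h score is not reconciled

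*Protocol*

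**What the plan says.** Under Outcome Measures, the pilot's preliminary efficacy criterion is met if the 80% "confidence interval for the between-group difference in average pain score in the 24-hour postoperative period favours LA block". The Statistical Analysis section repeats the 80% interval for the 24 h average. The Sample Size section supports about 30 patients with "Assuming a difference of 1 and standard deviation of 1.2", and claims a probability above 80% that the interval excludes zero.

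The NRS schedule appears among the definitive trial's secondary outcomes, but the pilot takes these over: "We will also collect the outcomes for the definitive trial to test and refine data collection processes". Scores are "measured at the standard time points of nursing care assessments": a preoperative baseline, then "four times per hour in PACU until discharge; if admitted, hourly for 2 hours, and then every 6 hours in the Inpatient Unit". The list closes with two single readings for all patients: "and at discharge from hospital; 24 hours after surgery is complete".

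Discharge within 24 h is foreseen. Opioid use is counted across the hospital units, ending with "Inpatient Unit, and home in the 24-hour period after completion of surgery", and "LOS includes time in the PACU, Surgical Day Care (SDC) and, if required, Inpatient Unit".

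The 24 h score is sourced in several places:
- Additional Details of Study Design first says, without condition, that it is taken from the chart. The same section then lists it as an entry in the Recovery Booklet diary, with a completion reminder at 3-4 days.
- Data Collection also assigns it to the booklet, and limits the Clinical Form's pain section to PACU and the inpatient ward.
- Confidentiality (Management of Non-Identifying Data) has the seven-day booklet finished before the patient leaves hospital.

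**The concern.** The criterion is meant to describe a full day of pain. For a same-day patient, the visible schedule observes the first hours closely, then nothing until one value at 24 h. A single-injection block may wear off in just that interval. A statistical analysis plan can choose weights and missing-data rules, but it cannot supply readings that nobody took.

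That makes the one late reading important, and its origin is unclear. A hospital chart would not hold a 24 h score for a patient already at home. A booklet entry could hold it, but the only stated reminder to complete the booklet comes days after the time point, so a late entry would rest on recall. At stake is whether the pilot's efficacy signal describes the 24 h effect or mainly the early effect.

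**Working it through.** **1. The plan's own figure.** Inputs from the protocol: difference 1, SD 1.2, about 30 patients randomised 1:1 (15 per arm), 80% two-sided interval (0.10 in each tail).
- Noncentrality: 1 / (1.2 × √(2/15)) = 2.282.
- Normal approximation: Φ(2.282 − 1.282) = 0.841.
- Noncentral t, 28 df: 0.833.

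The stated probability above 80% reproduces.

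**2. What is read, and when.**

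| Period | Admitted | Same-day discharge |
|---|---|---|
| PACU | 4 per hour | 4 per hour |
| After PACU | hourly for 2 h, then 6-hourly | discharge reading only |
| Discharge to 24 h | ward readings continue while in hospital | none visible |
| 24 h | one value | one value |

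**3. Length of the gap.** The protocol gives no PACU stay, discharge time or same-day rate. Assume a PACU stay of 1-3 h and discharge 1-4 h later. The last hospital reading then falls at 2-7 h, which leaves 24 − 7 = 17 h to 24 − 2 = 22 h without a reading before the 24 h value.

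**4. What the gap can do (illustration).** Assume a 1-point benefit that holds until T1, then falls linearly to 0 at T2. The true 24 h mean difference is (T1 + T2)/48. Apply the trapezoid rule (a time-weighted mean) to the available readings, with PACU to 2 h.

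| T1, T2 (h) | True | Discharge at 3 h | Discharge at 6 h | 3 h, plus home readings at 8, 12, 18 h | 3 h, plus home readings at 8, 16 h |
|---|---|---|---|---|---|
| 4, 8 | 0.25 | 0.56 | 0.40 | 0.23 | 0.23 |
| 6, 12 | 0.38 | 0.56 | 0.63 | 0.35 | 0.41 |
| 8, 16 | 0.50 | 0.56 | 0.63 | 0.52 | 0.50 |
| 12, 18 | 0.63 | 0.56 | 0.63 | 0.63 | 0.61 |
| 12, 24 | 0.75 | 0.56 | 0.63 | 0.75 | 0.72 |

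- Discharge at 3 h: every profile reads 1 up to 3 h and 0 at 24 h, so (3 + 21/2)/24 = 0.5625.
- Discharge at 6 h, first profile: the reading at 6 h is 0.5, so (2 + 4 × 0.75 + 18 × 0.25)/24 = 0.396. The other four still read 1 at 6 h, so (6 + 18/2)/24 = 0.625.

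Errors run from 0.56 − 0.25 = +0.31 to 0.56 − 0.75 = −0.19 with discharge at 3 h, and from +0.25 to −0.13 with discharge at 6 h. A constant effect of 1 returns 1.00 under every schedule, and no effect returns 0.

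**5. Effect on the criterion.** With 15 per arm and SD 1.2 (noncentral t), the probability that the interval favours the block is 0.236 at 0.25, 0.493 at 0.5625 and 0.657 at 0.75. These values take every patient as discharged the same day. With no effect it is 0.10, the nominal tail.

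**6. Sensitivity to the SD** (difference 1, 15 per arm): 0.833 at 1.2, 0.800 at 1.27 and 0.70 at 1.5.

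**The case against.** The strongest reply is that the visible text is not the whole schedule. The Appendix 5 figure of data collection timepoints and Forms 5, 6 and 11 are not shown, and the diary's layout is known only from summaries. This stands, so the gap can be asserted only for the text at hand. Both summaries of the booklet do mention pain at 24 h and no other time.

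A reader might infer that the chart and booklet statements flatly contradict each other, or that patients at home will have no 24 h value. The documents do not support that. A 24 h score is scheduled for everyone. Data Collection extends chart collection over the inpatient stay and allows access to the electronic record, so an admitted patient can have a 24 h chart score. The Confidentiality section even has the 24 h QoR-15 completed before discharge. Chart for inpatients and booklet for those at home is a sensible reading. What remains is that no sentence says so, and that the unconditional chart statement and the booklet being finished before discharge do not fit a patient who went home. Participants, ward nurses and research assistants are blinded and the score is patient-reported either way, so two sources do not by themselves bias the comparison.

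It is also fair to say that the sizes rest on assumed stays and waning curves. The identical 0.56 in five rows follows from profiles that all keep the full effect past 3 h and lose it by 24 h. The 6 h variant separates one of the five.

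**Conclusion.** The point holds in a limited form. On the visible text, the 24 h average for a same-day patient rests on the early hours plus one value at 24 h, and a waning effect in between can be misjudged in either direction. The illustrative error is roughly −0.2 to +0.3 of a point on an assumed 1-point initial effect. It applies only to the unknown share of patients who go home the same day. The source of the 24 h score needs reconciling across three sections.

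A reader might go further and conclude that the criterion is biased towards the block, or that the power statement is wrong. Neither follows. With no effect or a constant effect there is no bias, and the stated probability reproduces at 83-84%. How readings are weighted in the average may be left to the analysis plan and is not part of this point. Because this is a pilot intended partly to refine data collection, it is a worthwhile and inexpensive improvement rather than a fatal flaw.

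**What to change.** - Collect the 24 h NRS from every patient, prompted at 24 h together with the QoR-15 already due then. Name this as the source of the 24 h value.
- Reconcile Additional Details of Study Design, Data Collection and Confidentiality with that choice, including when and where the booklet is completed.
- Add two or three timed NRS entries between discharge and 24 h to the existing diary, for example at about 8, 12 and 18 h after surgery. In the illustration these bring the estimates to within about 0.02 of the true values; two entries at 8 and 16 h bring them to within about 0.04.
- If Appendix 5 or Form 5 already schedules home readings, say so in Outcome Measures instead.

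The cost is a sentence on source, a prompt and a few diary lines, with slightly more burden on patients. The SD of 1.2 should be re-checked for the resulting summary: at 15 per arm and a difference of 1, the probability stays at or above 80% only up to an SD of about 1.27.

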Furthermore, the COVID-19 pandemic has caused an unprecedented shift in pressures facing our healthcare system. Operating room closures and pauses in screening for certain conditions (eg. mammography for breast cancer) in the spring of 2020 resulted in a backlog of an estimated 30,298 surgical cases.⁶¹ As British Columbia enters a phase of surgical renewal to meet patient demand, finding ways to limit use of in-patient resources while providing safe surgical care remains more important than ever. In this context, the use of regional anesthesia such as the TPVB+ block is very timely. By enhancing multimodal perioperative analgesia, the TPVB+ block may reduce perioperative and postoperative opioid requirements, reduce patient symptoms that could delay discharge, and shorten overall length of hospital stay. This could maximize the efficient use of needed surgical resources, while preserving inpatient resources for treatment of COVID-19 patients.

Benefits for Patients

Patients may benefit from LA blocks (TPVB+) by requiring less total opioid analgesia in the perioperative period. Patients may report reduced postoperative pain scores, and may experience fewer side effects related to opioid consumption (nausea and vomiting). This may result in a shorter length of stay in hospital and improved overall quality of recovery. Furthermore, the reduction in acute pain may reduce the incidence of chronic pain.

The use of regional anesthesia (rather than general anesthesia alone) may reduce recurrent breast cancer risk, although this is currently under investigation.^{62,63}

Benefits for Researchers

The benefit to the plastic surgeon, general surgeon, and anesthesiologist will be knowledge of the patient-reported effectiveness as well as the postoperative and long-term morbidity of LA blocks as measured by total opioid analgesia in the perioperative period, patient-reported postoperative pain scores, side effects related to opioid consumption, reported quality of recovery and incidence of chronic pain. There may be an additional benefit of shorter length of stay in hospital, which has positive implications both for patients and for improved resource allocation within the health care system.

SECTION 2: METHODS [\(back\)](#)

Study Design [\(back\)](#)

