The design of the pilot RCT is the same as the future definitive trial, a parallel-group, double-blinded randomized controlled trial (RCT). The target population are patients undergoing mastectomy with IBR using tissue expanders or immediate implants. The intervention will be a local anesthetic regional block defined as a TPVB with Pecs 1 (TPVB+) using local anesthetic infiltrate. The local anesthetic block (LA block) will be compared to a placebo block (sham block) using normal saline infiltrate. Thus, each patient in this study will be assigned to receive either; 1) LA Block: TPVB and Pecs I block with local anesthetic infiltrate, or 2) sham block: TPVB and Pecs I block with saline infiltrate. The assignment of intervention will be determined by randomization through REDCap. The pilot trial will be conducted at Mount Saint Joseph Hospital (MSJH).

Each participant will be assigned a consecutive Study ID at time of enrollment. Patients will be randomized 1:1 to either LA or sham block. Patients undergoing symmetrizing procedures as part of a bilateral breast surgery will not have a regional block on the symmetrizing side (which is not IBR). Patients undergoing bilateral IBR surgery using implants or expanders on both breasts will not be included in the study due to risk of local anesthetic toxicity with bilateral TPVB+.

The randomization sequence will be created using REDCap-generated 1:1 randomization with permuted blocks of varying size (4 and 6). The assignments (LA or sham) will be placed in order in opaque, consecutively numbered envelopes. The sequence and envelopes will be created by an independent research assistant who will not be involved in the remainder of the study implementation.

Study participants, Operating Room (OR) anesthesiologists, surgeons, research assistants, and nurses in the OR, Post-anesthesia Care Unit (PACU), and ward will be blinded as to whether a participant receives LA block or sham block. At MSJH, the anesthesiologists in the operative theater are separate from the team of regional anesthesiologists performing regional blocks in the preoperative area. Only the regional anesthesiologist and anesthesia assistant in the preoperative block area will be unblinded to reduce the potential unnecessary risk of a pneumothorax with the sham saline TPVB. This will enable injection of saline just outside of the paravertebral space.

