Appendix 1: Nerve Block Protocol: TPVB+ (TPVB with Pec I block) [\(back\)](#)

All sham and LA blocks will be performed by a regional anesthesiologist experienced in performing TPVB and Pec I blocks. The blocks will be performed in the preoperative block room. Participants will be monitored as per existing site policy. The blocks will be done using sterile technique. Before and after each procedure, the ultrasound machine will be cleaned and disinfected using disinfectant wipes and allowed to air dry as per hospital/site policy.

1. Prior to the procedure, the patient will have the procedure explained to them, and consent documented as per hospital policy. Standard monitors and a safety check will be performed. Sedation medication (midazolam 1-2mg and fentanyl 25-50mcg) will be given.
2. The regional anesthesiologist will prepare syringes for injection of sham and regional anesthetic blocks depending on patient allocation.
3. Syringes for injection may include:
 - a. LA TPVB block: 25ml of 0.3% ropivacaine with 1:400K epinephrine
 - b. LA Pecs I block: 10ml of 0.3% ropivacaine with 1:400K epinephrine
 - c. Sham TPVB block: 25ml normal saline (0.9% NaCl)
 - d. Sham Pecs I block: 10ml normal saline (0.9% NaCl)
4. The skin at the planned injection site will be cleansed with 2% chlorhexidine solution or 1% iodine (10% povidone iodine) in case of chlorhexidine allergy.
5. Nonsterile conducting gel will be applied to the 9 MHz linear probe ultrasound transducer, and the transducer will be covered with a sterile drape.
6. The anesthesiologist will don a clean face mask and sterile gloves prior to handling sterile equipment or touching the sterile field.
7. Sterile ultrasound conducting gel will be applied to the skin.
8. Local anesthetic skin wheal will be raised with 1% lidocaine.
9. TPVB block: The T2/3 or 3/4 interspace will be determined by counting ribs with the ultrasound. The ultrasound probe will be placed in a sagittal orientation aiming to visualize the transverse processes. The location of the pleura will be noted and the LA will be injected in the paravertebral space incrementally after negative aspiration looking for pleural drift. For the sham injection the needle will be inserted to just superficial to the transverse process for an erector spinae plane injection (between erector spinae muscles and the transverse processes).

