10. Pecs I block: Infiltrate will be injected into the fascia between the pectoralis minor and pectoralis major muscles at the level of the 3rd rib in the mid-to-lateral 1/3 of the clavicle in a transverse to oblique orientation. Identification of the pectoral branch of the thoracoacromial artery will assist with needle placement. The needle will be inserted from medial/superior to lateral/inferior. Visual confirmation will be by ultrasound upon visualizing the separation of tissue layers with the injected infiltrate.
11. The needle and probe will be removed and the injection site wiped dry.
12. The patient will be continuously monitored in the block area until ready for transport to the operating room for surgery.

Appendix 2: Evidenced-Based Multimodal Perioperative Analgesia and Anti-emetic Management Protocol for Alloplastic Immediate Breast Reconstruction ([back](#))

PREOPERATIVE

- 1- Patient Education:
 - a. Information on options, risks/benefits, recovery ⁷³⁻⁷⁶
- 2- Fasting & Nutrition:
 - a. Allow clear fluids up to 2 hours before arrival to the hospital and no solid foods after midnight ^{26,77-79}
- 3- Preoperative Analgesics: ²¹ to be given in preop 30 minutes to 2 hours pre-induction
 - a. Gabapentin 600mg po x1 ^{27,80-84}
 - b. Acetaminophen 1000mg po x 1
 - c. Celecoxib 400mg po x 1²¹
 - d. Midazolam 1-4mg IV PRN during nerve block administration only
 - e. Fentanyl 25-100mcg IV PRN during nerve block administration only
- 4- Preoperative anti-emetics: to be given in block room
 - a. Dexamethasone 8mg IV ⁸⁵⁻⁹²
 - i. by Anesthesiologist in block room by slow infusion
- 5- Preoperative Antibiotics: to be given in block room
 - a. Preoperative antibiotics within 60 minutes of incision ⁹³
 - i. by Anesthesiologist in block room
- 6- Regional Anesthesia: Paravertebral block with Pecs I (TPVB+)^{57,94} (Intervention)
 - a. Paravertebral T3/4 block: 0.3% ropivacaine+1:400K epi x 25mL
 - b. Pecs I block with 0.3% ropivacaine with 1:400 epi x 10mL
 - c. TOTAL nerve block LA volume 0.3% ropivacaine x 35 mL = 105mg for 50kg patient

INTRAOPERATIVE

- 1- General Anesthesia
 - a. Induction with Propofol (2-4mg/kg IV), Fentanyl (1-4mcg/kg IV), Rocuronium (0.5-1.2mg/kg IV)
 - b. Endotracheal intubation
 - c. Maintenance with inhalational Sevoflurane (0.6-1.2 MAC)
 - d. Opioid as needed for hemodynamic stability (eg. Fentanyl 0.25-1mcg/kg IV boluses, Hydromorphone to maximum 2mg IV or Morphine to maximum 15mg IV)

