Appendix 3: Calculation of Morphine Milligram Equivalents (MME) ([back](#))

Opioid	To convert to oral morphine milligram equivalent (MME), multiply dose of drug (in mg) by:*
Codeine	0.15
Hydromorphone	5
Morphine	1
Oxycodone	1.5
Tramadol	0.15
*Conversion ratios for opioids can vary based on individual patient drug metabolism, which may be influenced by genetics and other medications.	
Fentanyl 0.01 (10mcg) IV = Equivalent to Morphine 5mg	

Table is adapted from National Guidelines for Opioid Conversion^{97,98} and local Health Authority Opioid Conversion Table for Fentanyl.⁹⁹

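### The opioid total omits fentanyl given in the preoperative block room, where the only unblinded staff work; that dose could differ by arm, though nothing shows that it does

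*Protocol*

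**What the plan says.** The secondary outcomes under Outcome Measures set the time window of the opioid outcome: "Opioid analgesia requirements during surgery and in the first 24 hours after surgery, defined as morphine milligram equivalents (MME"). The next sentence lists the places that are summed. It begins "The total MME will include intraoperative opioids administered in the OR and postoperative opioids administered/ingested in the Postanesthetic Care Unit (PACU"), continues through Surgical Day Care and the Inpatient Unit, and ends "and home in the 24-hour period after completion of surgery". The preoperative block room falls outside both the window and the list. The rescue-medication outcome does not pick it up either, since it starts in PACU.

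Appendix 1 places the block in the preoperative block room and states in step 1: "Sedation medication (midazolam 1-2mg and fentanyl 25-50mcg) will be given". Appendix 2, under preoperative analgesics, states: "Fentanyl 25-100mcg IV PRN during nerve block administration only".

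On blinding, Study Design says: "Only the regional anesthesiologist and anesthesia assistant in the preoperative block area will be unblinded". Operating-room anesthesiologists, surgeons, research assistants and nurses in the OR, PACU and ward are blinded.

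Benefits for Researchers describes the effect of the block "as measured by total opioid analgesia in the perioperative period". Objectives names opioid consumption in the primary objectives of the definitive trial, while Outcome Measures lists it as secondary. The Data Collection section has preoperative medications recorded on the Clinical Form.

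**The concern.** The outcome compares opioid use between arms. Opioid given in the OR, in PACU and on the ward is given by blinded staff. Block-room fentanyl is an opioid dose given where allocation is known, and it is the one left out of the total.

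Three features make it open to an arm difference without any deliberate bias:

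- The dose is a range, and as needed in Appendix 2.
- The staff in the room know the assignment.
- The needle goes into the paravertebral space in the local anesthetic arm but stops superficial to the transverse process in the sham arm.

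Fentanyl given shortly before induction may also reduce what the blinded OR anesthesiologist then needs to give. If one arm received more of it, part of that arm's opioid would sit in an uncounted room, and its counted OR opioid might fall as well. The comparison would then partly reflect where opioid was given rather than how much was needed.

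**Working it through.** The plan states no figure for this outcome, so there is none to reproduce. The check is what is left out, and how large it could be.

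**1. Coverage**

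| Setting | In the MME total? | Staff blinded? |
|---|---|---|
| Preoperative block room | No | No (regional anesthesiologist and assistant) |
| OR | Yes | Yes |
| PACU, ward | Yes | Yes |
| Home | Yes | Participant blinded |

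**2. Conversion.** Appendix 3 prints "Fentanyl 0.01 (10mcg) IV = Equivalent to Morphine 5mg". That is 5 / 10 = 0.5 MME per mcg.

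**3. Uncounted amount per patient**

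- Appendix 1 (25 to 50 mcg, worded as given to all): 25 × 0.5 = 12.5 MME, to 50 × 0.5 = 25 MME.
- Appendix 2 (25 to 100 mcg, as needed): 0 if unused; if used, 12.5 MME to 100 × 0.5 = 50 MME.

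For scale, one 10 mg oxycodone dose counts 10 × 1.5 = 15 MME.

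**4. Effect on the comparison.** Let B be block-room opioid and C the counted opioid. The complete arm difference is ΔB + ΔC and the reported one is ΔC, so reported minus complete = −ΔB. This holds whether or not block-room fentanyl displaces OR opioid. With full displacement, ΔC moves by −ΔB and the complete total does not move. With none, ΔC does not move and the complete total moves by ΔB.

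**5. Outer limits of ΔB.** These need every patient in one arm at one end of the range and every patient in the other arm at the other end, so they are bounds and not expectations.

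- Appendix 1: 50 − 25 = 25 mcg, or 12.5 MME.
- Appendix 2, all dosed: 100 − 25 = 75 mcg, or 37.5 MME.
- Appendix 2, one arm undosed: 100 mcg, or 50 MME.

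**6. A yardstick in mcg, free of the Appendix 3 factor.** The Pecs Block section reports mean fentanyl, control minus block, from cited trials of combined Pecs I and II block in modified radical mastectomy: intraoperative 218 − 141 = 77 mcg; postoperative 609 − 438 = 171 mcg; sum 248 mcg. The block and the surgery differ from this trial, so this gives rough scale only. The protocol gives no expected ΔB, so a range is assumed:

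| Assumed ΔB (mcg) | MME | % of 77 mcg | % of 248 mcg |
|---|---|---|---|
| 12.5 | 6.25 | 16 | 5 |
| 25 | 12.5 | 32 | 10 |
| 50 | 25 | 65 | 20 |
| 75 | 37.5 | 97 | 30 |

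The rows above 25 mcg are possible only under Appendix 2.

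**The case against.** The best reply is that the exclusion is deliberate and sound. The outcome measures requirement during and after surgery. Appendix 1 labels the block-room drugs as sedation for delivering the block, a need that the block itself cannot reduce. The perioperative wording comes from a benefits paragraph, not an outcome definition. This is a fair reason to keep the dose on its own line. It is weaker as a reason to leave it out of view, because the same drug is counted once the patient reaches the OR, and an earlier dose may change that count.

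The mechanism is also limited. In Appendix 1 sedation is step 1, syringe preparation step 2, the lidocaine skin wheal step 8, and needle depth first differs at step 9. A dose given wholly at step 1 cannot respond to that difference. Both arms receive the same volumes (25 mL and 10 mL), and Study Design says all other parameters are identical. What remains is the choice within a dose range, and the Appendix 2 wording, which allows dosing while the block is being done.

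A reader might infer more than the text supports:

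- *That the local anesthetic arm will look opioid-sparing because its fentanyl is hidden.* No passage gives an arm difference or its direction; more fentanyl in the sham arm would work the other way.
- *That unblinded staff are documented as giving the drug.* This follows from place and timing but is not stated.
- *That the dose is lost.* It is recorded as a preoperative medication; only the total omits it.
- *That every patient has 12.5 to 50 MME uncounted.* This joins the universal dose of Appendix 1 to the as-needed upper limit of Appendix 2.

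Tabulating preoperative drugs by arm could be left to an analysis plan that is not shown. The definition of the total, however, is fixed in the protocol.

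**Conclusion.** The point holds as a gap in an outcome definition, not as a demonstrated bias. As written, a between-arm opioid comparison leaves out a discretionary opioid dose given where allocation is known. The size rests on the Appendix 3 factor as printed and on which appendix applies; the MME figures scale with that factor, while the mcg comparisons do not depend on it. The actual effect equals the arm difference in block-room dose, which may be zero.

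The consequence for the pilot is small. Its progression criteria are enrolment, block success, retention and the 80% interval for 24-hour pain, and none uses the opioid total. It matters more for the definitive trial, whose primary objectives name opioid consumption and whose outcomes the pilot collects in order to refine data collection. This is a worthwhile, inexpensive improvement.

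**What to change.** In the opioid outcome under Outcome Measures, add opioids given in the preoperative block room to the settings in the MME total, and extend the time window to match. Report block-room opioid by arm as its own line, and give the total with and without it. A reader who regards it as procedural sedation can then use the narrower figure.

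Reconcile the fentanyl statements in Appendix 1 (25 to 50 mcg, worded as given) and Appendix 2 (25 to 100 mcg, as needed). Which is right is for the investigators to settle; no dose is proposed here.

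The cost is a phrase in the definition and one table row, from data already due on the Clinical Form. The downside is a slightly larger total that includes some procedural sedation. The sample size and the progression criteria do not change.
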